6.6 Analysis of Influenza Infection

Influenza infection during the study is an exploratory endpoint, and the analyses of influenza infection confirmed by RT-PCR test may be performed using the FAS.

Due to the ongoing COVID-19 pandemic, participants may get infected with SARS-CoV-2 or experience symptoms consistent with influenza-like illness (ILI) during the study.

NP swab samples will be collected from all participants before the injection on Day 1 for assessment of asymptomatic infection with respiratory pathogens, including influenza virus and SARS-CoV-2, as influenza or COVID-19 symptoms may confound reactogenicity assessment. Furthermore, if a participant experiences any signs or symptoms suggesting ILI and/or COVID-19, an additional NP swab sample will be collected to confirm the diagnosis via RT-PCR.

A CDC-defined ILI is defined as body temperature $\geq 37.8^{\circ}\text{C}$ (100°F) accompanied by cough and/or sore throat. An RT-PCR confirmed ILI is defined as a positive influenza result by RT-PCR done at any setting during the study period.

Summaries below will be provided, unless otherwise specified.

- RT-PCR test results at baseline will be summarized by test and vaccination group. Participants with positive influenza results at baseline will be presented in a listing.
- The number and percentage of participants with at least one positive influenza result at post-baseline will be provided by vaccination group. Participants with at least one positive influenza result at post-baseline will be presented in a listing.

6.7 Interim Analysis

One interim analysis (IA) is planned in this study. It will be performed after participants have completed the Day 29 visit.

This interim analysis will be focused on providing insight on the primary study objectives using the available data.

The IA will include safety and immunogenicity and will be performed after participants have completed the Day 29 visit. All data relevant to the IA through the Day 29 visit will be cleaned (i.e., data that are as clean as possible).

A limited number of Sponsor and CRO personnel will be unblinded to perform the IAs. Please refer to the DBP for more details on the blinding of IA.

An independent, unblinded statistics team will carry out the IA. The unblinded statistics team will not be involved in either study design or the regular study conduct. The study site staffs, investigators, study monitors, and participants will remain blinded until after the final database lock for final analysis.

6.8 Internal Safety Team Review

The safety monitoring for this study will include a group of blinded study team members, inclusive of, at a minimum, a Sponsor medical monitor, a CRO medical monitor, a blinded IST, and an unblinded DSMB.

The IST will comprise Sponsor physicians. The IST will conduct a scheduled review of safety data after approximately 96 participants (12 per study arm) have completed the Day 8 visit as well as ad hoc safety data reviews if requested by the study team. Enrollment will continue while these reviews are conducted if no pause rules have been met and the study team has not identified any safety concerns.

The IST will also conduct ad hoc reviews as requested by the study medical monitor and the study team. Details regarding the IST composition, responsibilities, procedures, and frequency of data review will be defined in the mRNA-1020-P101 Internal Safety Team (IST) Charter.

6.9 Data Safety Monitoring Board Review

An independent unblinded DSMB will be used throughout the conduct of this study. This committee will be composed of independent members with relevant therapeutic and/or biostatistical expertise to allow for the ongoing unblinded review of safety data from this study population.

The DSMB will conduct unblinded reviews of safety data on an ad hoc basis if any pause rule is met or as requested by the study team and /or IST.

The DSMB will also review unblinded IA results provided by the independent unblinded statistician.

A secure file transfer path will be decided between the CRO and Sponsor to use for the transfer of unblinded study data for DSMB review. Only the CRO independent unblinded

biostatistician, unblinded programmer(s), unblinded medical monitor (if assigned for unblinded DSMB review), and unblinded Sponsor clinical representative (if assigned for unblinded DSMB review) will have access to upload the unblinded data package to the secured file transfer location to be delivered to the DSMB. Refer to the mRNA-1020-P101 Data Safety Monitoring Board (DSMB) Charter for more details.

6.10 Subgroup Analysis

The protocol does not define any formal subgroup analyses, and the study is not adequately powered to perform formal subgroup analyses. However, age-specific subgroup analyses may be performed to explore for potential differences in safety/reactogenicity or immune responses across age groups.

7 CHANGES FROM PLANNED ANALYSES IN PROTOCOL

Not applicable.

9 LIST OF APPENDICES

9.1 *Appendix A Standards for Safety and Immunogenicity Variable Display in TLFs*

Continuous Variables: The precision for continuous variables will be based on the precision of the data itself. The mean and median will be presented to one decimal place more than the original results; the SD will be presented to two decimal places more than the original results; the minimum and maximum will be presented to the same precision as the original results.

Categorical Variables: Percentages will be presented to one decimal place.

9.2 *Appendix B Analysis Visit Windows for Safety and Immunogenicity Analysis*

Safety and Immunogenicity Analysis will be summarized using the following analysis visit window for post injection assessments:

Step 1: If the safety and immunogenicity assessments are collected at scheduled visit, i.e., nominal scheduled visit, the data collected at scheduled visit will be used.

Step 2: If the safety and immunogenicity assessments are not collected at the scheduled visit, assessments collected at unscheduled visit will be used using the analysis visit windows described in [Table 4](#) below.

If a participant has multiple assessments within the same analysis visit, the following rule will be used:

- If multiple assessments occur within a given analysis visit, the assessment closest to the target study day will be used.
- If there are 2 or more assessments equal distance to the target study day, the last assessment will be used.

Table 4 Analysis Visit Window

Visit	Target Study Day	Visit Window in Study Day
Labs		
Day 8	8	[2, 18]
Immunogenicity		
Day 1	1 (Date of Vaccination)	1, Pre-vaccination
Day 8	8	[2, 18]
Day 29	29	[19, 105]
Day 181	181	≥ 106

9.3 *Appendix C Imputation Rules for Missing Prior/Concomitant Medications and Non-Study Vaccinations Dates*

Imputation rules for missing or partial medication start/end dates are defined below:

1. Missing or partial medication start date:

- If only Day is missing, use the first day of the month, unless:
 - The medication end date is after the date of injection or is missing AND the start month and year of the medication coincide with the start month and year of the injection. In this case, use the date of injection.
- If Day and Month are both missing, use the first day of the year, unless:
 - The medication end date is after the date of injection or is missing AND the start year of the medication coincide with the start year of the injection. In this case, use the date of injection
- If Day, Month, and Year are all missing, the date will not be imputed, but the medication will be treated as though it began prior to the injection for purposes of determining if status as prior or concomitant.

2. Missing or partial medication end date:

- If only Day is missing, use the earliest date of (last day of the month, study completion, discontinuation from the study, or death).
- If Day and Month are both missing, use the earliest date of (last day of the year, study completion, discontinuation from the study, or death).
- If Day, Month, and Year are all missing, the date will not be imputed, but the medication will be flagged as a continuing medication.

In summary, the prior, concomitant, or post categorization of a medication is described in [Table 5](#) below.

Table 5 Prior, Concomitant, and Post Categorization of Medications and Non-Study Vaccinations

Medication Start Date	Medication End Date		
	< Injection Date of IP	\geq Injection Date and \leq Injection Date + 27 Days	> Injection Date + 27 days [1]
< Injection date of IP [2]	P	P, C	P, C, A
\geq Injection date and \leq Injection date + 27 days	-	C	C, A
> Injection date + 27 days	-	-	A

A = Post; C = Concomitant; P = Prior

[1] includes medications with completely missing end date

[2] includes medications with completely missing start date

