3 STUDY ENDPOINTS

3.1 Primary Endpoints

Safety

- Frequency and grade of each solicited local and systemic reactogenicity adverse reaction (AR) during a 7-day follow-up period post-vaccination
- Frequency and severity of any unsolicited adverse events (AEs) during the 28-day follow-up period post-vaccination
- Frequency of any serious adverse events (SAEs), adverse events of special interest (AESIs), medically attended adverse events (MAAEs), and AEs leading to withdrawal from Day 1 through Day 181/end of study (EoS)
- Safety laboratory abnormalities through 7 days post-vaccination

Immunogenicity

- Geometric mean titer (GMT) and geometric mean fold rise (GMFR) at Day 29 compared with Day 1 (baseline) and percentage of participants with seroconversion, defined as a Day 29 titer $\geq 1:40$ if baseline is $< 1:10$ or a 4-fold or greater rise if baseline is $\geq 1:10$ in anti-hemagglutinin (HA) antibodies measured by hemagglutination inhibition (HAI) assay
- GMT and GMFR of anti-neuraminidase (NA) measured by neuraminidase inhibition (NAI) assay at Day 1 and Day 29 and percentage of participants with a change in the Day 29 titer of at least 2-/3-/4-fold rise, defined as $\geq 2-/3-/4$ -fold of

the lower limit of quantification (LLOQ) if the Day 1 titer is < LLOQ; or $\geq 2\text{-}3\text{-}4\text{-}$ fold of the Day 1 titer if the Day 1 titer is \geq LLOQ

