6.2.7 Unscheduled Visits and Visit Windowing Rules

Unscheduled visit measurements will be included in analysis as follows:

- In scheduled visit windows per specified visit windowing rules.
- In the derivation of baseline/last on-treatment values.
- In the derivation of max/min on-treatment values and max/min change from baseline values for safety analyses.
- In individual participant data listings as appropriate.

The analysis visit windows for protocol-defined visits are provided in [Appendix B](#).

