6.4.4 Clinical Laboratory Evaluations

Safety laboratory testing will include hematology and serum chemistry.

For continuous hematology and serum chemistry parameters, the observed values and changes from baseline will be summarized at each time point by vaccination group and then by age group as defined in [Section 6.2.9](#).

Summary of Grade 3+ laboratory abnormalities by visit and toxicity grades will be provided by vaccination group and then by age group as defined in [Section 6.2.9](#).

Hematology and chemistry toxicity grades will be summarized using a shift table from baseline to Day 8 by vaccination group.

All laboratory test results will be presented in the data listings. The results that are outside the reference ranges will be flagged in the data listings. The abnormalities meeting the toxicity grading criteria (Grade 3 or higher) in [Appendix E](#) in any safety laboratory (hematology and serum chemistry) will be listed separately.

A pregnancy test will be performed on all female participants of childbearing potential at the Screening Visit and before vaccine administration on Day 1 via point-of-care urine, and as needed at unscheduled visits (urine or blood pregnancy test based on the investigator's discretion).

The pregnancy test results will be listed.

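### When the scheduled Day 8 laboratory sample exists, Appendix B keeps earlier unscheduled values out of the Grade 3+ and shift tables, so those tables can understate a primary safety endpoint

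*SAP*

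**What the plan says.** SAP 3.1 defines the primary laboratory endpoint over a period: "Safety laboratory abnormalities through 7 days post-vaccination".

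SAP 9.2 (Appendix B) decides which value represents each visit. In Step 1, when the assessment was made at the nominal visit, "the data collected at scheduled visit will be used". Step 2 adds: "If the safety and immunogenicity assessments are not collected at the scheduled visit, assessments collected at unscheduled visit will be used". If several values compete within one analysis visit, "the assessment closest to the target study day will be used", and the last one is taken if two are equally close. For laboratories, Table 4 of the SAP has a single post-injection row: Day 8, study days 2 to 18.

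SAP 6.4.4 plans two graded laboratory tables: "Summary of Grade 3+ laboratory abnormalities by visit and toxicity grades will be provided by vaccination group" (and then age group), and "Hematology and chemistry toxicity grades will be summarized using a shift table from baseline to Day 8 by vaccination group". It also lists all laboratory results, with a separate listing of Grade 3 or higher abnormalities.

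SAP 6.2.7 brings unscheduled values into visit windows under the windowing rules, which leads back to Appendix B. It also uses them "In the derivation of max/min on-treatment values and max/min change from baseline values for safety analyses". No laboratory table in 6.4.4 reports a maximum, a minimum or a worst grade.

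**The concern.** The endpoint asks whether an abnormality occurred at any time in the period. The tables answer a narrower question: what grade the one selected Day 8 value had. The two answers differ when an abnormality is found early on an unscheduled sample and has resolved by the scheduled one.

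The protocol gives reason to care about that pattern. Section 2.3.2 says that laboratory abnormalities, including liver function increases, were seen with similar mRNA vaccines and moved back toward baseline over time. Unscheduled sampling is foreseen: Section 8.1.7 allows blood tests at illness visits, Section 8.2 allows unscheduled samples for safety reasons, and Section 8.4.4 mentions follow-up of abnormal laboratory results.

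Pause rules 2 and 7 (protocol Tables 5 and 6) count Grade 4 and Grade 3 laboratory abnormalities that cannot reasonably be attributed to another cause, and are not limited to the scheduled sample. A value that counted toward a pause could thus be missing from the same arm's Grade 3+ laboratory table.

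**Working it through.** **Sampling.** Protocol Table 1 schedules safety laboratories at screening and Day 8 only. The Day 8 window is -2 or +1 days, that is, study days 6 to 9.

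**The rule applied to simple cases** (G = toxicity grade):

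| Samples in the [2, 18] window | Appendix B uses | Worst grade |
|---|---|---|
| Day 4 unscheduled G3; Day 8 scheduled G0 | G0 | G3 |
| No scheduled sample; Day 4 unscheduled G3; Day 8 unscheduled G0 | G0 | G3 |
| No scheduled sample; Day 4 unscheduled G3 only | G3 | G3 |
| No scheduled sample; Day 16 unscheduled G3 only | G3, shown as Day 8 | G3 |

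The second row is plausible because protocol Section 8.4.14 asks for a clinically significant abnormal value to be repeated until it is normal or stable.

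**All day combinations.** Take a scheduled G0 on Day 6, 7, 8 or 9 and an unscheduled G3 on each of Days 2 to 8: 4 x 7 = 28 combinations. Appendix B returns G0 in all 28. The unscheduled sample is strictly earlier than the scheduled one in 4 + 5 + 6 + 7 = 22 of them, on the same day in 3, and later in 3.

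Dropping Step 1 and keeping only the closest-to-target rule would recover 4 of 28 (scheduled/unscheduled days 6/7, 6/8, 7/8 and 9/8, taking the scheduled sample as the later of two on one day). Only one of those four, 9/8, has the unscheduled sample first. Removing Step 1 is therefore not a sufficient remedy; the summary has to use the worst grade.

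**Size of one case.** With 70 per arm, 1/70 = 1.43 percentage points. In an age stratum of 35, 1/35 = 2.86 points.

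**The plan's own figure.** SAP 4.3 gives the chance of at least one event in 70 participants as about 76% at 2% incidence and 94% at 4%. The formula is 1 - (1 - p)^70: 1 - 0.98^70 = 75.7% and 1 - 0.96^70 = 94.3%. Both reproduce.

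**Illustration.** Suppose a fraction f of participants with a Grade 3+ value have it only on an omitted draw. The by-visit table then sees incidence p(1 - f). The documents give no f; the range is assumed.

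| f | p = 2% | p = 4% |
|---|---|---|
| 0 | 75.7% | 94.3% |
| 10% | 72.0% | 92.3% |
| 25% | 65.3% | 88.1% |
| 50% | 50.5% | 75.7% |

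For example, at p = 2% and f = 25%, 1 - (1 - 0.015)^70 = 65.3%. A worst-grade table keeps the f = 0 row.

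**The case against.** The strongest reply is that such a value has other routes into the report. A clinically significant abnormal result must be recorded as an adverse event (protocol 8.4.14), laboratory abnormalities are counted among unsolicited events (SAP 6.4), and a low platelet count is an event of special interest (protocol Appendix 3). These events are tabulated by arm in SAP 6.4.1 without the Appendix B windows. Every Grade 3+ result is also listed separately. This stands, and it limits the loss to values not reported as adverse events. It does not remove the gap, because reporting rests largely on the investigator's judgment, whereas the grade tables apply fixed thresholds.

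Second, no safety sample is scheduled between dosing and Day 8, and follow-up of an abnormal laboratory result would normally come after the Day 8 result. The affected group may be very small or empty. This also stands. The 28 combinations show what the rule does, not how often it matters.

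Third, tabulation by time point follows protocol Section 9.5.2, the study is descriptive, and the table shells are not available, so an any-post-baseline row cannot be ruled out. The SAP text does not plan one, however.

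A reader might go further and infer that an early unscheduled draw always signals a clinical problem, or that the expected Grade 3+ rate is near zero. Neither is documented: Section 8.2 also allows repeat samples for technical reasons, and no expected rate is given. Nor is the [2, 18] window a serious fault in itself, since an unscheduled Day 10 to 18 value enters only when the scheduled sample is missing.

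**Conclusion.** The point holds as a minor gap between a period endpoint and single-visit tables. When the scheduled Day 8 sample exists, earlier unscheduled values cannot enter either graded table. When it is missing, a recovered value can still displace the worst one. The maximum and minimum derivations in SAP 6.2.7 do not help, because neither table uses them.

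A reader might conclude that every such value is confined to listings, or that the primary endpoint is shown to be understated. The documents support neither. Confinement to listings applies to values not reported as adverse events, and understatement is possible, not demonstrated. Each omitted case is worth 1.4 percentage points of a planned arm. The total effect depends on the unknown frequency of unscheduled draws and is probably small.

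**What to change.** In SAP 6.4.4, base the Grade 3+ summary and the shift table, or an added worst-post-vaccination row in each, on the worst toxicity grade among:

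- the scheduled Day 8 sample, whenever it was drawn; and
- all unscheduled post-vaccination samples up to the Day 8 visit.

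If the scheduled sample is missing, use the worst grade among unscheduled samples in the existing [2, 18] window, and flag values after the protocol's Day 8 window (after study day 9). Keep the Appendix B scheduled-first rule for means and changes from baseline. The SAP should also state how it treats an unscheduled sample drawn after an early Day 8 visit but still inside the protocol window.

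A hard cut-off at study day 9 should be avoided: it would remove a nominal Day 8 sample drawn late, which Step 1 now keeps.

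The cost is one new derivation and slightly higher reported abnormality rates; no new data are needed. The grade is not already available from SAP 6.2.7, which covers values and changes, not grades. It must be derived per parameter and direction, since SAP Appendix E grades white cells both high and low, and hemoglobin by level and by change from baseline.

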9.4 Appendix A Imputation Rules for Missing AE Dates

Imputation rules for missing or partial AE start dates and end dates are defined below:

1. Missing or partial AE start date:

- If only Day is missing, use the first day of the month, unless:
 - The AE end date is after the date of the injection or is missing AND the start month and year of the AE coincide with the start month and year of the injection. In this case, use the date and time of the injection, even if time is collected.
- If Day and Month are both missing, use the first day of the year, unless:
 - The AE end date is after the date of the injection or is missing AND the start year of the AE coincides with the start year of the injection. In this case, use the date of the injection
- If Day, Month and Year are all missing, the date will not be imputed. However, if the AE end date is prior to the date of the injection, then the AE will be considered a pre-treatment AE. Otherwise, the AE will be considered treatment-emergent.

2. Missing or partial AE end dates will not be imputed.

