Any AE considered serious by the Investigator or that meets SAE criteria (Section 8.4.2) must be reported to the Sponsor immediately (within 24 hours of becoming aware of the SAE) via the EDC system. The Investigator will assess whether there is a reasonable possibility that the IP caused the SAE. The Sponsor will be responsible for notifying the relevant regulatory authorities of any SAE as outlined in 21 US CFR Parts 312 and 320. The Investigator is responsible for notifying the institutional review board (IRB) directly.

If the eCRF is unavailable at the time of the SAE, the following contact information is to be used for SAE reporting:

• SAE Mailbox: PPD

• SAE Hotline (USA): PPD

• SAE Fax Line (USA): PPD

Regulatory reporting requirements for SAEs are described in Section 8.4.17.

The Investigator and any qualified designees are responsible for detecting, documenting, and recording events that meet the definition of an AE, including SAEs, and remain responsible for following up AEs that are serious, considered related to the IP or study procedures, or that caused the participant to discontinue the study.

8.4.13. **Reporting of Adverse Events of Special Interest**

The following process for reporting an AESI ensures compliance with 21 CFR 312 and ICH GCP guidelines. After learning that a participant has experienced an AESI, the Investigator or designee is responsible for reporting the AESI to the Sponsor, regardless of relationship or expectedness, within 24 hours of becoming aware of the event. If the AESI meets the criteria for an SAE, the SAE reporting procedure should be followed.

8.4.14. Time Period and Frequency for Collecting Adverse Event and Serious Adverse **Event Information**

Medical occurrences that begin before the start of IP administration but after obtaining informed consent will be recorded on the Medical History/Current Medical Conditions section of the eCRF and not in the AE section; however, if the condition worsens at any time after IP administration during the study, it will be recorded and reported as an AE.

Adverse events may be collected as follows:

- Observing the participant.
- Receiving an unsolicited complaint from the participant.
- Questioning the participant in an unbiased and nonleading manner.

Solicited ARs will be collected from the day of vaccination through 6 days after injection. Other (unsolicited) AEs will be collected from the day of vaccination through 28 days after the injection.

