6.4.1 Unsolicited Adverse Events

An unsolicited AE is any AE reported by the participant that is not specified as a solicited AR in the protocol or is specified as a solicited AR but starts outside the protocol-defined period for reporting solicited ARs (i.e., for the 7 days after the injection of IP).

Only treatment-emergent AE (TEAE) will be included in the analysis. A TEAE is defined as any event occurring during the study not before exposure to study vaccine or any event already present that worsens in intensity or frequency after exposure to study vaccine.

AEs will also be evaluated by the investigator for MAAE and AESI. An MAAE is defined as an AE that leads to an unscheduled visit to a healthcare practitioner (HCP). An AESI is an AE (serious or nonserious) of scientific and medical concern specific to the Sponsor's product or program, for which ongoing monitoring and immediate notification by the Investigator to the Sponsor are required. The AESIs for this study are listed in [APPENDIX 3](#) of the protocol Section 11.3.

Unsolicited AEs within 28 days after vaccination will be summarized by vaccination group. Unsolicited SAE, unsolicited AESI, unsolicited MAAE, and unsolicited AE leading to withdrawal from the study up to 28 days after vaccination and overall period will be summarized by vaccination group. See [Section 6.2.9](#) and [Section 6.2.6](#) for definitions of analysis groups and analysis period respectively.

All summary tables (except for the overall summary of AEs) for unsolicited TEAEs will be presented by SOC and/or PT, and by SOC and PT and severity, with counts of participants included. SOCs will be displayed in internationally agreed order. PTs will be displayed in descending order of frequency of total in each vaccine type group and then alphabetically within SOC. When summarizing the number and percentage of participants with an event, participants with multiple occurrences of the same AE or a continuing AE will be counted once. Participants will be presented according to the highest severity in the summaries by severity, if participants reported multiple events under the same SOC and/or PT.

Percentages will be based upon the number of participants in the Safety Set within each vaccination group.

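### SAP 9.4 dates an AE before injection when its start is known only to the injection month or year and it ended on the injection day, and it does not say how a partial end date in that same period is compared with injection.

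*SAP*

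**What the plan says.** The rules are in SAP 9.4, Imputation Rules for Missing AE Dates (Appendix D in the SAP's table of contents).

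- **Start day unknown.** The default is "If only Day is missing, use the first day of the month, unless" a two-part condition holds: "The AE end date is after the date of the injection or is missing AND the start month and year" of the AE match those of the injection. If it holds, the injection date is used.
- **Start day and month unknown.** The rule is parallel. The default is 1 January, and the condition is the same but matched on year.
- **Start date fully unknown.** No date is imputed. The text continues: "However, if the AE end date is prior to the date of the injection, then the AE will be considered a pre-treatment AE". Every other such AE is treatment-emergent.
- **End dates.** "Missing or partial AE end dates will not be imputed".

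SAP 6.4.1 gives the consequence: "Only treatment-emergent AE (TEAE) will be included in the analysis". Its definition of a TEAE also keeps events already present that worsen after vaccination.

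For medications, SAP 9.3 (Appendix C) does impute partial end dates: "If only Day is missing, use the earliest date of (last day of the month, study completion, discontinuation from the study, or death").

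**The concern.** The condition that rescues an AE from the first-of-month default names two cases only: an end date strictly after injection, and a missing end date. Two kinds of record are not covered.

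1. **The end date is the injection date.** It is neither later than injection nor missing, so the default applies. The fully-unknown branch sends the same AE the other way. Knowing the start month therefore turns a treatment-emergent event into a pre-treatment one.
2. **The end date is partial and lies in the same period as the injection**, for example start and end both known only as April for an April injection. SAP 9.4 neither completes the end date nor says whether it counts as missing. Two programmers could code this in opposite ways.

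Unsolicited AEs within 28 days, and SAEs, AESIs and MAAEs through the end of study, are primary safety endpoints (SAP 3.1). Protocol 8.4.14 says that occurrences beginning after consent but before injection "will be recorded on the Medical History/Current Medical Conditions section of the eCRF and not in the AE section". A record on the AE page should therefore usually be a post-injection onset or a worsening, and errors from this rule run mostly towards undercounting.

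**Working it through.** The plan gives no figure on this point, so there is none to reproduce. The check applies the rule as written.

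**Inputs.** From SAP 9.4: the default, the condition, and the non-imputation of partial end dates. Assumptions: an illustrative 30-day month (April 2022), injection on each day from 1 to 30, and an AE start known only to the injection month. A partial end date is read in two ways: (a) it counts as missing; (b) it is neither missing nor shown to be after injection.

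**Step 1. Injection days on which the imputed start falls before injection**

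| End date on record | Reading (a) | Reading (b) |
|---|---|---|
| On the injection day | 29/30 | 29/30 |
| One day after injection | 0/30 | 0/30 |
| Missing | 0/30 | 0/30 |
| Partial, injection month | 0/30 | 29/30 |
| Partial, next month | 0/30 | 0/30 |

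The one exception in each 29/30 is injection on the 1st. The first row does not depend on the reading; the fourth depends on it entirely.

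**Step 2. Example.** Injection is on 15 April and the AE ended on 15 April.
- Start known as April: imputed 1 April, study day 1 − 15 = −14.
- Start known only as 2022: imputed 1 January. From 1 January to 15 April is 31 + 28 + 31 + 14 = 104 days, so study day −104.
- Start fully unknown: the end date is not before injection, so the AE is treatment-emergent.

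**Step 3. Size of the partial-date gap.** Take AEs with start and end both known only to the month. Assume injection day *d* uniform on 1–30, onset study day *s* uniform on 1–28, and an end *k* days after onset. There are 30 × 28 = 840 combinations. Under reading (b) an AE is pre-dated if *d* > 1 and *d* + *s* − 1 + *k* ≤ 30, so each *d* from 2 to 30 contributes min(28, 31 − *d* − *k*) combinations, or none if that is negative.

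- *k* = 0: 28 + (28 + 27 + … + 1) = 28 + 406 = 434; 434/840 = 51.7%
- *k* = 3: 26 + 25 + … + 1 = 351; 351/840 = 41.8%
- *k* = 7: 22 + 21 + … + 1 = 253; 253/840 = 30.1%

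Under reading (a) all three are 0%. These are shares of AEs dated only to the month, not of all AEs.

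**Step 4. One participant.** A lost participant is 1/70 = 1.4 percentage points of an arm, or 1/35 = 2.9 points of an age stratum, if the lost AE was that person's only event in the table row.

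**Step 5. The proposed wording.** With *on or after*, and a partial end date accepted unless its whole period precedes injection, the first and fourth rows become 0/30 under both readings. An AE that ended the day before injection is still pre-dated on 29 of 30 days, as it should be. The remaining day is injection on the 1st, where an AE that began in that month cannot have ended the day before.

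**The case against.** The strongest reply is that few records can be affected.

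- **Same-day gap.** A post-injection AE that ended on the injection day must have started that day, so a query would normally settle its start. Participants are observed for at least 60 minutes (Protocol 6.3.2), and time of onset is collected for unsolicited AEs (Protocol 8.4.11). Solicited reactions are analysed in the Solicited Safety Set and do not pass through the TEAE flag (SAP 6.4.3).
- **Partial dates.** SAP 9.4 is silent; it does not direct pre-injection dating. A partial end in a later month is plainly after injection.
- **Presumption of post-injection onset.** Protocol 8.4.8 provides for separate analysis of AEs before receipt of product, and SAP 9.4 has a pre-treatment class, so an AE-page record is not certain to be post-injection.
- **Appendix C.** Its start-date rule uses the same strict condition, so it shares the same-day gap. Only its handling of partial end dates is better.

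All of this stands, and it limits the size. It does not remove the contradiction between the branches or supply the missing comparison rule. On the partial dates, SAP 9.3 and 9.4 list missing and partial as separate categories while the condition names only missing, which makes the adverse reading at least as natural as the other.

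A reader might infer that post-vaccination events drop out of every TEAE table. The documents do not support that: the worsening limb keeps some events, and the gap arises only when the known start month or year is that of injection. Nor do they support citing 30–52% as the loss, since the other reading gives 0%.

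**Conclusion.** The point holds in limited form. For an AE that ended on the injection day, SAP 9.4 gives a pre-injection start date on its literal text, and its own fully-unknown branch contradicts that result. For a partial end date within the injection month (or known only to the injection year), the result is undefined: before injection on one reading, on the injection date on the other.

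The likely effect is a slight downward bias in the unsolicited TEAE summaries. Among AEs with start and end known only to the month, the share pre-dated runs from 0% to about 30–52%, depending on the reading and on the uniform-date and duration assumptions above. The documents do not say how many AEs have partial dates, and the number is probably small. The study is descriptive and tests no hypothesis, so this is a correction to the prespecified rule and not a threat to the design.

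A reader might also infer that every AE with a fully unknown start should be given the injection date. SAP 9.4 does leave unstated whether such AEs enter the 28-day tables, but that remedy does not follow. It could, for example, move an undated MAAE first reported at the Day 151 call into the 28-day period.

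**What to change.** In SAP 9.4:

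1. In both partial-start rules (day unknown; day and month unknown), require the end date to be *on or after* the injection date, or missing.
2. Add that a partial end date meets the condition unless the whole period it covers lies before injection.

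This brings both rules into line with the fully-unknown branch. AEs shown to have ended before injection stay pre-treatment.

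The cost is a few words and the matching derivation code. The downside is that a few events of uncertain onset, some of which may have begun before injection, will be counted as TEAEs, so the reported AE rate may be slightly higher.
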